3.5 Statistical analysis plan and power calculation

The power analysis for the clinical study of RETENTION is based on a similar analysis performed for the TIM-HF-2 evaluating a telemonitoring intervention² with similar endpoints and considering similar inclusion criteria:

- Chronic heart failure New York Heart Association (NYHA) class II or III
- Echocardiographically determined left ventricular ejection fraction (LVEF) ≤45%
- Hospitalisation due to decompensated HF within the last 12months before randomisation
- Depression score PHQ-9<10

For the sample size calculation, TIM-HF-2 used data for specific subgroups from the TIM-HF trial for sample size calculations. For the patient subgroup that mirrored the population they did include in the TIM-HF-2 trial, 19 days were lost due to all-cause death or unplanned cardiovascular hospital admissions at 12 months

² Koehler F, Koehler K, Deckwart O et. al. Lancet. 2018 Sep 22;392(10152):1047-1057. doi: 10.1016/S0140-6736(18)31880-4. Epub 2018 Aug 25. PMID: 30153985.

in the usual care group, and 12 days were lost for patients in the remote patient management group, which corresponds to a 38% reduction. The estimated standard deviation (pooled) was 48 and based on that they calculated that 750 patients would be required in each group to detect this difference with a power of 80% and a two-sided α of 5%.

For RETENTION we expect a slightly higher decrease in the endpoint (40%). If we apply the same rate of losses TIM-HF trial for control group(19 days per year) to a follow up period of 18 months, we expect a mean of 29 (19+10) days lost due to all-cause death or unplanned cardiovascular hospital admissions in the usual care group and 17 days lost in the test group (-40% of 29). Under these assumptions, the number of patients for each group of the study should be 199 (398 in total). Hence, accounting for about 10% of attrition rate and loss to follow up, the recruitment target for the study has been set to 450 patients.

Group sample sizes of 199 and 199 achieve 80% power to reject the null hypothesis of equal means difference with a standard deviation for both groups of 48 and with a significance level (alpha) of 0,05 using a one-sided test.

Statistical analysis plan

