- Demographic, clinical, and device data, and treatment results will be summarised using descriptive summary statistics. Data collected in the trial will be summarised overall and by treatment groups. Continuous variables will be presented with the numbers of observations, means, standard deviations, minimums, and maximums. For comparisons, the difference between the groups will be summarised with the difference of the two means together with 95% confidence intervals and tested using the two-sample t-test. These calculations will be done under the assumption that the data for the two groups are independent and approximately gaussian in distribution. If asymptotic assumptions fail, nonparametric summary statistics (medians, 25th and 75th percentiles) may be displayed. In addition, more appropriate non-parametric tests will be considered if the assumptions for the parametric tests are violated. For the comparison of two independent samples, if the data are not normally distributed, Mann-Whitney rank sum test will be performed instead of the parametric t-test,
- For categorical variables results will be summarised with subject counts, percentages. The differences between the two treatment groups will be summarised with the difference in percent and compared using the chi-square test or Fisher's exact test as appropriate.
- Survival analysis techniques will be used to analyse the time-to-event variables.

The primary analyses will compare the days lost due to unplanned cardiovascular hospitalisations or all-cause death and the survival free from death or unplanned hospitalisation/ambulatory administration of intravenous therapy between interventions group and usual care group by the means of the parametric t-test or non-parametric rank sum test as mentioned above.

To evaluate the additional measure of the primary outcome, the survival free from the combined endpoint, survival curves will be constructed using Kaplan-Meier estimates. Log-rank test results will also be computed for comparison of survival distributions between intervention and usual care groups.

Pre-specified subgroup analyses include:

- The three patient categories (HF, LVAD and HT)
- Males and Females
- Patients with a hospitalisation less than three months from the enrolment

• Patients older than 60 years

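### The 80% power rests on a one-sided 5% test that does not match the planned 95% confidence interval; a two-sided 5% test gives about 70%

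*Protocol*

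**What the plan says.** All the relevant text is in protocol Section 3.5.

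- **Source calculation.** The power analysis is said to build on that of an earlier telemonitoring trial, which found 750 patients per group for 19 versus 12 days lost and a pooled standard deviation of 48, "with a power of 80% and a two-sided α of 5" per cent.
- **This trial's sample size.** The control mean assumed over the 18-month follow-up is 29 days lost, against 17 in the test group. The power statement reads "Group sample sizes of 199 and 199 achieve 80% power to reject the null hypothesis of equal means difference". The SD is taken as 48 in each arm, and the error rate is given as "a significance level (alpha) of 0,05 using a one-sided test". No reason is given for moving from two-sided to one-sided.
- **Analysis.** For continuous variables, the group difference is to be "summarised with the difference of the two means together with 95% confidence intervals and tested using the two-sample t-test", with the Mann-Whitney test as the alternative if the data are not normal. The paragraph on the primary analyses refers back to these tests. Neither place states an alpha or a sidedness.

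**The concern.** The section states a one-sided 5% test for sizing and a 95% confidence interval for reporting. For a difference in means, a 95% interval is conventionally two-sided and corresponds to a two-sided 5% test. The interval that corresponds to a one-sided 5% test is the two-sided 90% interval, or equivalently a one-sided 95% bound. As written, the test and the interval can therefore disagree on the primary endpoint, and nothing in the section says which one decides.

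Two things are at stake. If the one-sided 5% test decides, benefit can be claimed with a 5% chance of error under no effect, against 2.5% in that direction under the two-sided standard of the source trial, and the reported 95% interval may include zero. If the test is run two-sided, as the interval and the unqualified test names would lead most analysts to do, the stated 80% power does not apply. Leaving the question open also allows sidedness to be chosen after the data are seen.

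**Working it through.** **Inputs (all from protocol Section 3.5).** Control mean 29 days, test mean 17 days, so δ = 12. SD σ = 48 in both groups. n = 199 evaluable per arm. α = 0.05. The recruitment target is 450, or 225 per arm.

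**1. Reproduce the plan's figure (one-sided).**
Normal approximation: n = 2(z₀.₉₅ + z₀.₈₀)²σ²/δ² = 2 × (1.645 + 0.842)² × (48/12)² ≈ 198 per arm. The exact calculation with the non-central t distribution gives 199 per arm, with power 80.1%. The protocol's 199 is reproduced.

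**2. Same design, two-sided 5%.**

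| Evaluable per arm | One-sided 5% | Two-sided 5% |
|---|---|---|
| 199 | 80.1% | 70.1% |
| 225 (no attrition) | 84.2% | 75.4% |

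(Non-central t; the normal approximation at 199 gives 80.2% and 70.3%.) For 80% two-sided power, n = 2 × (1.960 + 0.842)² × (48/12)² ≈ 252 by the normal approximation and 253 per arm by the exact t.

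**3. Detectable difference at 199 per arm, two-sided, 80% power.**
SE = 48 × √(2/199) = 4.81 days. Detectable δ ≈ (1.960 + 0.842) × 4.81 ≈ 13.5 days, or 13.5/29 ≈ 46% of the control mean. The plan assumes 12 days.

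**4. Where the test and the interval disagree.**
With 396 degrees of freedom the critical values are 1.649 (one-sided) and 1.966 (two-sided).
- One-sided 5% is reached at 1.649 × 4.81 ≈ 7.9 days.
- The 95% interval excludes zero only from 1.966 × 4.81 ≈ 9.5 days.

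An observed benefit between these limits is significant one-sided while the 95% interval includes zero. If the design assumptions hold, the chance of landing there is 80.1% − 70.1% = 10 percentage points.

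**5. Check that the source calculation was two-sided.**
With δ = 19 − 12 = 7 and σ = 48, the normal approximation gives 739 per arm two-sided and 582 one-sided. The reported 750 fits the two-sided figure.

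**The case against.** The strongest reply is that nothing has been miscalculated or hidden. The one-sided test is declared, and 199 per arm follows from it. That stands, and it makes this an inconsistency within Section 3.5, not an arithmetic error.

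It can also be said that the analysis text never uses the word two-sided. This is true: two-sidedness there is the conventional reading of a 95% interval and an unqualified two-sample test. A reader might infer that the protocol states two different error rates. It does not. The only sidedness stated for this trial's own test is one-sided. But on that reading the 95% interval is the element that does not fit, so the text needs correcting either way.

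Next, the 95% interval appears in a general statement on continuous variables, and an interval may be reported for estimation beside a one-sided test. That is fair. The disagreement affects the conclusion only if the interval is read as evidence for or against benefit, but with nothing saying otherwise it will be read that way. Nor does building on the earlier trial oblige the sponsor to copy its alpha; the effect size and follow-up were changed too. Those changes, however, are explained and the change of sidedness is not.

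A reader might also infer that a one-sided test is ruled out because the stated aim is only to investigate an effect. The documents do not support that: Section 3.5 expects a 40% reduction and Section 3.3.2 anticipates improved outcomes, so a directional expectation is present. The point does not depend on this.

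Finally, a separate statistical analysis plan might settle sidedness. The protocol nevertheless fixes alpha, sidedness, interval level and test within one section, and these should agree there.

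**Conclusion.** The point holds as an inconsistency. The 80% power at 199 per arm is obtained only with a one-sided 5% test, which does not match the planned 95% interval in its usual two-sided sense and departs without explanation from the two-sided alpha of the source calculation. Tested two-sided at 5%, the same design has about 70% power, and about 75% even if all 225 per arm are evaluable.

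These figures take the protocol's own 12 days, SD of 48 and a t-test as given. Using the unrounded 40% effect (0.40 × 29 = 11.6 days) lowers power at 199 per arm slightly, to about 78% one-sided and 67% two-sided. It is not shown that the one-sided calculation is wrong, or that a one-sided test is inadmissible in this trial. The matter still needs settling before the data are unblinded, because the primary conclusion could turn on it.

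**What to change.** In Section 3.5, state that the primary test is two-sided at 5%, in agreement with the 95% confidence interval. Restate the power as about 70% for 12 days with SD 48 at 199 per arm (about 75% at 225 per arm with no attrition), and give the difference detectable with 80% power as about 13.5 days.

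If the sponsor keeps the one-sided 5% test, the analysis text should say so, justify it, and base the decision on the matching one-sided 95% bound (the lower or upper limit of a two-sided 90% interval, according to the direction of the difference).

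Either route is a change of wording with no change in enrolment. The cost of the first is a less favourable stated power. Restoring 80% two-sided would be a separate decision: 253 evaluable per arm, which after 10% attrition is 253/0.9 ≈ 281 per arm, or roughly 560 recruited instead of 450.

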3.2 Study design and endpoints

3.2.1 Study design

The aim of this study is to investigate the effect of introducing daily and environmentally aware patient monitoring protocols outside hospitals and interventions informed by it, on all-cause and cardiovascular mortality, heart failure hospitalisations or emergency room visits, and quality of life in patients with symptomatic chronic heart failure (HF), patients with implanted Left Ventricular Assist Device (VAD) and heart transplant (HT) recipients.

Patient specific measures related to the vitals (including weight, blood pressure, heart rate, peripheral capillary oxygen saturation), daily physical activity, quality of sleep (as expressed through heart rate variability), psychological state and nutrition intake will be collected. In addition, the study will collect real world data derived from non-medical sources regarding environmental factors in the living environment of patients participating in the study (i.e., ambient temperature, relative humidity, pollutants).

The data will be collected through a Randomised Clinical Trial (RCT) where the aforementioned groups of patients, between 18 and 75 years of age, will be observed in an outpatient setting through the remote monitoring platform of RETENTION, which will be created for this purpose, and the standard clinical practice. A total of 450 participants will be recruited to participate in the study. 30-35% of the recruited patients will be women. This is because up until now, women have been underrepresented in most heart failure clinical trials, despite the fact that disease prevalence remains generally the same between both sexes. When it comes in heart failure with reduced ejection fraction, subgroup analysis of several trials reveals that women were older, more likely to have pre-existing hypertension and less likely to have coronary artery disease. In addition, despite heavier symptom burden, women fared better in survival and hospitalisation risk. LVAD implantation has also been studied mainly on male patients with the added restriction of smaller ventricular dimensions rendering device support unavailable in women.

A control group of patients of similar age dispersion will also be set up and followed up only by the standard means and procedures currently employed as best practices. This will be a multi-centre RCT conducted at six clinical centres in Greece, Italy, Germany and Spain.

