Randomisation: A total of 450 participants will be recruited to participate in the study, all of whom are treated according to standard heart failure care protocols. All patients will be provided with monitoring devices and home sensors to collect the data required by the study. Data will be collected continuously from all the participants. Half of the participants (Test group, n=225)data, collected through the provided devices, will be made available to treating physicians for review and additional interventions as determined by the analysis of these data may be done according to the judgement of the treating physician. In the rest of the participants (control group, n=225), treating physicians will be blinded to the data collected through the RETENTION platform and therefore no additional interventions will be done. Randomisation will be conducted centrally. Randomisation will be conducted centrally through the RETENTION platform.

Randomisation will be stratified by centre and type of patients (heart failure, LVAD and heart transplant) with a block size of 4.

Duration¹: It is re-estimated that instead of eight (8), fourteen(14) months will be required to collect all the essential documents from all participating sites, prepare the files for submission to Ethics and Regulatory authorities in all four countries in order to obtain the appropriate approvals later on, by M20, instead of M18 that was originally planned. Upon receipt of ethics approvals from all sites, sites will be activated within one (1) month. Patient recruitment will start in month 20 of the project and will last for ten (10) months. Following recruitment and randomisation, each participant will be monitored in an outpatient setting through the remote monitoring platform of RETENTION for a period of 18 months. Over this period, each participant will have regular follow ups with clinic visits (upon registration/randomisation, and at months4,8,12 and 18) in addition to the clinic visits required by the standard heart failure management protocols. All clinic visits can be performed within ±15 days from the expected date. Upon completion of patient monitoring period, three (3) months will be needed for activities related to the termination of the study (e.g., for final analysis of the data collected by the study).

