3.4 Subjects / Population(s)

3.4.1 Definition of sub-populations if subgroup analysis is intended

There will be two groups of patients. The first group will be subject to remote monitoring through the RETENTION platform but no additional intervention will be given other than the standard follow-up practice as it has been performed in the participating clinical centres during the last decade. The second group will be monitored and followed up on using the remote monitoring platform, and additional interventions will be provided as the system evolves with time based on the data analytics. All participants will take part in the clinical study after detailed explanation of the project's aims and their participation requirements. They will receive an information leaflet and will sign an informed consent form. They will be able to leave the clinical study at any point without any kind of explanation necessary. All participants will be assessed at baseline, and at months 4,8,12 and 18.

A total of 450 patients across the six hospitals will participate in the project. These patients will include:

- 200 patients with HF not enlisted for transplant at the time of their recruitment (approximately 44% of the total number of patients)
- 150 LVAD patients (approximately 34% of the total number of patients)

100 heart transplant recipients (approximately 22% of the total number of patients)

Of these patients 225 patients will be the test group, referred to as remote patient monitoring and interventions group (RPMI group), and 225 patients will be the control group, referred to as remote patient monitoring and usual care (RPMUC group). The control and the test group for each site will have equal numbers of recruits in each of the above three categories of patients. Of the recruited patients 30-35% will be women. This is because up until now, women have been underrepresented in most heart failure clinical trials, despite the fact that the disease prevalence remains generally the same between both sexes. The individual clinical units which will participate in the study are expected to recruit the numbers of patient shown in Table 1.

Table 1: Recruitment targets for individual clinical partners and countries							
Partner	Clinical Unit	No of Patients	Country				
OCSC	OCSC	100	Greece				
NKUA	NKUA	80	Greece				
UNIBO	UNIBO	100	Italy				
UKESSEN	UKESSEN	100	Germany				
SERMAS	Hospital Universitario Ramón y Cajal (SERMAS-HURC)	70	Spain				

4 5 Ta

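### Randomisation is stratified by centre and patient type, but the t-test, rank-sum and log-rank comparisons name no strata; this gives up a modest, essentially free gain in precision

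*Protocol*

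**What the plan says.** **Design.** Protocol section 3.2.1: "Randomisation will be stratified by centre and type of patients (heart failure, LVAD and heart transplant) with a block size of 4". The same section says: "This will be a multi-centre RCT conducted at six clinical centres in Greece, Italy, Germany and Spain". Three patient types at six centres give up to 18 strata. Section 3.4.1 repeats the intention: "The control and the test group for each site will have equal numbers of recruits in each of the above three categories of patients".

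**Analysis.** Section 3.5, under its statistical analysis plan heading, has continuous variables "tested using the two-sample t-test", with this rider: "These calculations will be done under the assumption that the data for the two groups are independent and approximately gaussian in distribution". If the data are not normal, "Mann-Whitney rank sum test will be performed instead of the parametric t-test". The primary comparison is made "by the means of the parametric t-test or non-parametric rank sum test as mentioned above". For the additional measure of the primary outcome, Kaplan-Meier curves are drawn and "Log-rank test results will also be computed for comparison of survival distributions between intervention and usual care groups".

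None of these sentences carries a stratum, covariate or centre term. Patient type returns in section 3.5 only as a subgroup. Centre does not return at all.

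**The concern.** Blocks within strata hold the arms nearly equal in each centre-by-type cell. Differences between cells then contribute almost nothing to the chance difference between arms. A plain two-sample test does not know this: its pooled variance still contains the between-cell spread. Its standard error is therefore larger than the design warrants, its intervals are too wide, and its true type I error sits below the nominal level.

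The three populations have separate eligibility criteria in section 3.4.2, so it is plausible that patient type predicts days lost. At stake is precision that the stratified randomisation has already secured and that the named tests leave unused. The validity of the result is not at stake.

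**Working it through.** **Inputs from section 3.5.** Mean days lost 29 (usual care) and 17 (test), difference 12; SD 48 in both groups; one-sided alpha 0.05; 199 per group. **Input not in the protocol:** R², the share of the variance of days lost explained by centre and type. I assume 0 to 0.15.

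**1. The plan's own figure.** n per arm = 2 × 48² × (1.645 + 0.842)² / 12² = 198 by the normal approximation. The noncentral t gives 199 (power 80.1%). The stated 199 reproduces. It rests on the total SD and an unstratified test.

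**2. Standard errors.**
- Reported by the plain t-test: SE_u = 48 × √(2/199) = 4.812.
- True SE under stratified blocks, which a model with the strata also estimates: SE_a = 4.812 × √(1 − R²).
- Overstatement: SE_u / SE_a = 1/√(1 − R²).

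**3. Power, like for like.** Both tests are evaluated under the stratified design actually used, with z = 1.645 one-sided or 1.960 two-sided:
- unadjusted: Φ((12 − z × SE_u) / SE_a)
- adjusted: Φ(12 / SE_a − z)

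Worked at R² = 0.15, one-sided: SE_a = 4.812 × 0.922 = 4.437. Unadjusted: (12 − 1.645 × 4.812) / 4.437 = 0.921, so 82.1%. Adjusted: 12 / 4.437 − 1.645 = 1.060, so 85.5%.

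| R² | SE_u / SE_a | True one-sided alpha, unadjusted | One-sided power, unadjusted / adjusted | Two-sided power, unadjusted / adjusted |
|---|---|---|---|---|
| 0 | 1.000 | 0.050 | 80.2% / 80.2% | 70.3% / 70.3% |
| 0.05 | 1.026 | 0.046 | 80.8% / 82.0% | 70.8% / 72.5% |
| 0.10 | 1.054 | 0.042 | 81.5% / 83.7% | 71.3% / 74.8% |
| 0.15 | 1.085 | 0.037 | 82.1% / 85.5% | 71.9% / 77.2% |

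**4. What such R² would take (illustration, assumed means).** With the planned mix of 200 HF, 150 LVAD and 100 transplant patients, type means of 28/41/14 days give a between-type variance of about 98. Against 48² = 2304 that is R² of about 4%. Means of 21/53/9 days average 29 and give (200 × 8² + 150 × 24² + 100 × 20²) / 450 = 309. R² is then 309/2304 = 13% if 48 is the total SD, or 309/(2304 + 309) = 12% if it is the within-type SD.

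**5. Simulation check.** Normal data, 18 strata, blocks of 4, 398 patients, 3,000 runs per setting, the Spanish target of 70 assumed split 35/35. Power was 80.2% unadjusted against 81.2% adjusted at R² = 0.05, and 81.5% against 83.7% at 0.10. One null setting (R² = 0.10) gave an unadjusted type I error of 0.051, above the formula's 0.042; a longer run of that setting came back close to the formula. As a stress case beyond the assumed range, R² = 0.20 gave a mean reported SE of 4.81 against an empirical 4.3 to 4.4, and a one-sided type I error of 0.031.

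**6. Rank-sum and log-rank tests.** The same argument gives the same direction. I put no size on these, because the protocol gives neither the distribution of days lost nor event rates by patient type.

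**The case against.** The strongest reply is that nothing is broken. The unstratified t-test is valid and conservative, the estimate is unbiased, and the sample size was worked out for that very test with the total SD. On the protocol's own terms it reaches at least 80%. All of this stands.

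It can also be said that R² is unknown and could be zero. That stands too: the mismatch is certain, its cost is not.

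A third reply is that a separate statistical analysis plan may add the strata, and that section 3.5 leaves room by referring to survival analysis techniques and to more appropriate non-parametric tests. This stands in part for the secondary time-to-event endpoints. It does not cover the primary comparison, where section 3.5 names the tests itself.

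Stronger readings that a reader might infer, and why they fail:
- **That the mismatch makes the trial underpowered.** The 80% was planned one-sided and is kept. Two-sided power is about 70% because of the one-sided choice, which is a separate matter.
- **That adjustment lifts two-sided power from 70% to 77%.** That sets an unadjusted test at R² = 0 against an adjusted one at R² = 15%. Under the same stratified design the step is 71.9% to 77.2%.
- **That the pooled log-rank test pulls a hazard ratio towards 1.** Section 3.5 plans no hazard ratio and no Cox model, so there is no such estimate to distort.
- **That the sentence on independent, approximately gaussian data is itself the error.** It says nothing about strata. The point rests on the randomisation sentence set against the primary-analysis and log-rank sentences.

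**Conclusion.** The point holds as a matter of efficiency. The named comparisons ignore the randomisation strata, and for the primary t-test the standard error is 0 to about 8.5% too large for R² of 0 to 15%. Against an adjusted analysis the loss at R² of 5 to 15% is 1.2 to 3.4 power points one-sided (82.0 − 80.8 and 85.5 − 82.1), or 1.7 to 5.3 points two-sided (72.5 − 70.8 and 77.2 − 71.9). At R² = 0 it is nil.

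These figures assume normal data, equal variances, one treatment effect across strata and an R² that the protocol does not supply. The direction is secure if the strata predict outcome; the size is only indicative, most of all if the rank-sum test is used. There is no bias, no type I inflation and no shortfall against the planned one-sided 80%.

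**What to change.** In section 3.5, state that the between-arm comparisons account for the randomisation strata:

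- **Days lost:** a linear model with treatment, patient type and centre; a van Elteren test as the rank-based version.
- **Event-free survival:** a log-rank test stratified by patient type.
- **Small strata:** with up to 18 cells, some will be small. Keep patient type as the stratum and take centre as a covariate, or pool centres by a rule written down in advance.
- **Sensitivity:** keep the unstratified t-test, rank-sum and log-rank tests.

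The cost is analysis wording and code. Centre and patient type are needed to randomise, so they are already recorded, and the sample size need not change. Fixing the model before data are seen also avoids a later choice between adjusted and unadjusted results.

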3.2.2 Primary and secondary endpoints

The **primary study outcome** will be the days lost (%) due to unplanned cardiovascular hospitalisations or allcause death, comparing remote patient monitoring and interventions (RPMI) group with remote patient monitoring and usual care (RPMUC) group only during the individual follow-up time.

As additional measure of this primary outcome we will report the freedom from the combined occurrence of death or unplanned hospitalisation/ambulatory administration of intravenous (IV) diuretics, IV antibiotics, or intravenous (IV) steroids.

The secondary end-points include:

a. All-cause mortality during the individual follow-up time (to a maximum of 575 days, i.e., the 547 days of the patient monitoring period plus 28 days from the final study visit)

b. Cardiovascular mortality during the individual follow-up time (to a maximum of 575 days, i.e., the 574 days

¹ A delay of 5+ months was encountered in the completion of the present document D8.2, in relation to the study protocol and the evaluation framework. This delay inevitably affects the progress of the next project phases and will eventually result in a time shift for platform completion. At the time of submission of the present deliverable, the estimated minimum shift is ~3 months, therefore the onset of the trial study is shifted from the originally planned M19 to M22, and will end at M48 instead of 45, at the earliest. Accordingly, all trial internal phases are shifting as well, following the new estimated plan.

- of the patient monitoring period plus 28 days from the final study visit)
- c. Time to first unplanned HF hospitalisation
- d. Time to first unplanned cardiovascular hospitalisation
- e. Total unplanned HF hospitalisations (recurrent event analysis)
- f. Total unplanned cardiovascular hospitalisations (recurrent event analysis)
- g. Days (%) lost due to HF hospitalisations during the individual follow-up time.
- h. Number of smart device alarm notifications.

i. Change in the Kansas City Cardiomyopathy Questionnaire score between baseline (i.e., when a patient enters the study) and month 18.

j. Change in the levels of N-terminal pro-B-type natriuretic peptide (NT-proBNP) between baseline and month 18.

k. Change in the Depression Score Patient Health Questionnaire 9 (PHQ-9) score between baseline and month 18.

I. Change in the Heart Failure Caregiver Questionnaire (HF-CQ version 5.0) between baseline and month 18.

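### Section 3.5 lists event-free survival among the primary analyses and gives it a t-test or rank-sum test, contradicting Section 3.2.2 and its own Kaplan-Meier and log-rank plan

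*Protocol*

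**What the plan says.** Section 3.2.2 defines one primary outcome, which "will be the days lost (%) due to unplanned cardiovascular hospitalisations or allcause death". The composite comes next, at a lower rank: "As additional measure of this primary outcome we will report the freedom from the combined occurrence of death or unplanned hospitalisation/ambulatory administration" of intravenous treatment.

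The statistical analysis plan inside Section 3.5 then says three things about the composite.

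- Its general rules assign survival techniques to time-to-event variables.
- The sentence on the primary analyses joins the two measures: "The primary analyses will compare the days lost due to unplanned cardiovascular hospitalisations or all-cause death and the survival free from death" or the hospitalisation/intravenous-treatment component, "between interventions group and usual care group by the means of the parametric t-test or non-parametric rank sum test as mentioned above".
- The paragraph after it reads "To evaluate the additional measure of the primary outcome, the survival free from the combined endpoint, survival curves will be constructed using Kaplan-Meier estimates", followed by "Log-rank test results will also be computed for comparison of survival distributions between intervention and usual care groups".

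The only significance level set for this trial is in the sample-size text of Section 3.5: 0.05, one-sided, applied to days lost.

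**The concern.** Freedom from the composite is a time-to-event measure. A participant who reaches 18 months without an event, or who withdraws before then, has a censored time. A t-test or rank-sum test on observed times cannot tell such a time from an event on that day, so early withdrawal counts as early failure.

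Censoring before month 18 is expected. Section 3.5 allows for about 10% attrition, and Section 4.5 excludes data collected after withdrawal of consent from any analysis. Unequal withdrawal is plausible, because clinicians see and act on notifications in the test group only (Sections 3.7.4 and 3.7.5).

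The text also leaves two competing tests for one endpoint, with the log-rank test worded as an addition, and two statements of that endpoint's rank. If the two tests disagree, the protocol does not say which one counts.

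**Working it through.** **1. The plan's own figure.** Section 3.5 gives means of 29 and 17 days (difference 12), SD 48, one-sided alpha 0.05 and power 80%.

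n per group = 2 × (1.645 + 0.842)² × 48² / 12² = 2 × 6.18 × 16 ≈ 198, against 199 stated. Power at 199 per group is 80.2%. The trial is sized on days lost alone, and the composite plays no part in the calculation.

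**2. The statements side by side.**

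| Place | Rank of the composite | Test of the composite |
|---|---|---|
| 3.2.2 | additional measure, to be reported | none given |
| 3.5, general rules | – | survival techniques (all time-to-event variables) |
| 3.5, sentence on primary analyses | one of the primary analyses | t-test or rank-sum |
| 3.5, next paragraph | additional measure | Kaplan-Meier, log-rank |

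The sentence on primary analyses stands alone against the other three.

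**3. What the wrong test would do.** From the protocol: 225 per arm and 547 days of monitoring. Assumed, because the protocol does not give them: 30% or 50% of control participants with an event by day 547, and the split of withdrawal between arms, averaging 10%. Event times are exponential with rate −ln(1 − p)/547, withdrawal times likewise with rate −ln(1 − w)/547, and all times are cut at 547 days. Each test is two-sided at 5%. The table shows the percentage of simulated trials that reject.

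| Situation | Events | t-test | rank-sum | log-rank |
|---|---|---|---|---|
| No effect, withdrawal 10% v 10% | 30% | 4.6 | 4.4 | 4.6 |
| No effect, withdrawal 10% v 10% | 50% | 5.2 | 5.0 | 5.7 |
| No effect, withdrawal 12% v 8% | 50% | about 7 | about 7 | about 5 |
| No effect, withdrawal 15% v 5% | 30% | 27.8 | 32.6 | 5.6 |
| No effect, withdrawal 15% v 5% | 50% | 16.9 | 18.7 | 5.4 |
| HR 0.7, withdrawal 10% v 10% | 30% | 29 | 35 | 47 |
| HR 0.7, withdrawal 10% v 10% | 50% | 53 | 59 | 67 |

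With 2,000 runs the Monte Carlo standard error is at most √(0.25/2000) = 1.1 percentage points. Repeat runs moved single entries by up to about 4 points (log-rank power 67% to 71% with 50% events, for example) without changing the pattern. Inflation is worse with fewer events, because more of the observed times are then censoring times.

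**4. Error rate if either endpoint could succeed.** For two independent tests at 5%: 1 − 0.95² = 9.75%. For two one-sided 5% tests with assumed correlation 0.5, 0.7 or 0.9: 8.8%, 8.0% or 6.8%. This applies only under a success rule that the protocol does not contain.

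**The case against.** The strongest reply is that this is one badly joined sentence, and that the right method is already in the protocol. Survival techniques are assigned to this endpoint twice, once by the general rule and once by name. That stands: the fault is a contradiction about which test counts, and a valid test is not absent.

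A second reply is that type I error holds when withdrawal is equal. With a fixed 18-month follow-up and similar drop-out, the t-test and rank-sum test keep about 5%, and at 11% versus 9% they stay below 6% (50% events). That also stands. The inflation needs unequal withdrawal, and 15% versus 5% is an unfavourable assumption. The loss of power does not need imbalance. The power figures are for two-sided tests; at the one-sided 5% of the sample-size text, with 50% events, they are about 67% (t-test), 73% (rank-sum) and 80% (log-rank), so the gap remains.

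A reader might go further and infer from the plural in the sentence on primary analyses that the trial has two primary endpoints, each with its own 5% chance of success. The documents do not support that. Section 3.2.2 names one primary outcome, the paragraph after the disputed sentence again calls the composite an additional measure, the only alpha belongs to days lost, and no text lets either result establish success. A formal testing order may also be left to a separate statistical analysis plan, which is not at hand, so its absence is not part of this point.

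**Conclusion.** The concern holds as an internal contradiction with a wrong test attached. Section 3.5 disagrees with Section 3.2.2 on the status of event-free survival, and with its own other text on how to test it.

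If the disputed sentence were followed, the cost at equal 10% withdrawal would be power: about 8 to 14 points with 50% events (67% down to 59% or 53%) and 12 to 18 points with 30% events (47% down to 35% or 29%), at a hazard ratio of 0.7. Type I error would stay near 5% in that case. It would rise to about 7% at 12% versus 8% withdrawal (50% events), and to roughly 17% to 35% at 15% versus 5% across repeated runs. Log-rank stays at about 5% throughout. These sizes rest on assumed event rates, withdrawal splits and hazard ratio. The unsuitability of the tests for censored times does not.

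An overall error of about 7% to 10% would arise only if either endpoint were allowed to establish success at 5%. The present text should exclude that reading, but it does not state it.

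**What to change.** In Section 3.5:

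- Delete event-free survival from the sentence that specifies the t-test or rank-sum test, and put that sentence in the singular, so that days lost is the single primary analysis.
- In the next paragraph, make the log-rank test, shown with Kaplan-Meier curves, the only between-group test of the composite, and remove the wording that presents it as an addition.
- State that the composite is supportive and cannot by itself establish success, in line with Section 3.2.2.

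The edits touch only a few sentences and should be made before outcome data by group are seen. The sample size stays at 199 per group before attrition. The one small cost is that the composite cannot carry a success claim. A Cox hazard ratio and a formal testing order are optional.

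If the sponsor does want two primary endpoints, the alpha must be divided explicitly. An equal split (one-sided 0.025 each) would raise the requirement for days lost to 252 per group, or leave 75.5% power with the planned 225 per group and no losses.
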